12. DATA AND SPECIMEN BANKING* N/A

13. Data Safety and Monitoring Plan*

Suicidality questions will be asked in real-time during the participants enrollment in the acute care setting. If participant has identified suicide risk and treatment team is currently unaware, research staff will notify treatment team of suicide risk.

See grant: "DATA SAFETY AND MONITORING PLAN" (p.14) for further details.

14. Plans to Monitor Trial Performance, Including Fidelity and Integrity of the Data*

We will adhere to Investigator Guidance: Prompt Reporting Requirements (HRP-801). See grant: "DATA SAFETY AND MONITORING PLAN" (p.14-15) for details.

15. WITHDRAWAL OF SUBJECTS WITHOUT THEIR CONSENT*

Due to the sensitive nature of the topics discussed during the interview (behavioral health, substance use), the investigator's discretion will be used in deciding continued participation in the study.

16. RISKS TO THE SUBJECTS*

See grant: "HUMAN PARTICIPANTS PROTECTION" (p.19) "Potential Risk" and "Adequacy of the Protections Against Risk" for details.

17. POTENTIAL DIRECT BENEFITS TO SUBJECTS*

See grant: "HUMAN PARTICIPANTS PROTECTION" (p.20) "Potential Benefits of Proposed Research to Research Participants and Others" for details.

18. VULNERABLE POPULATIONS*

This study does not specifically recruit the vulnerable populations listed by NIH

supplemental grant instructions (i.e., pregnant women, human fetuses and neonates, prisoners, or children), and it does not exclude pregnant women and human fetuses and neonates. The study involves brief counseling, referral to treatment, and a mobile application that does not have restrictions in terms of safe use by vulnerable or other persons. No inducement, monetary or otherwise, will be offered to terminate a pregnancy. Individuals engaged in the research will have no part in any decisions as to the timing, method, or procedures used to terminate a pregnancy. Individuals engaged in the research will have no part in determining the viability of the neonate.

19. MULTI-SITE RESEARCH*

N/A

20. COMMUNITY-BASED PARTICIPATORY RESEARCH*

N/A

21. SHARING OF RESEARCH RESULTS WITH SUBJECTS*

It will be several years before the results of the research are available. If the subjects would like us to try to reach them at that time, we will request that they let us know during the consent process.

22. SETTING

We will recruit participants from two UMass Memorial Medical Center hospitals, including EDs, inpatient medical units, inpatient behavioral health units, (University and Memorial campuses), community acute care partners, and will refer participants to either the UMass Bridge Clinic, the CleanSlate Addiction Treatment Center, SaVida Health, Eleanor Health, Right Choice, and Spectrum Health Systems—outpatient MOUD clinics based on their preference. Patient interviews will be conducted in a private setting such as in an ED or inpatient treatment room or private consultation room. Clinician training and interviews will also be conducted in a private office or remotely via Zoom and will not be recorded. Data analysis will be completed in a private office on a secure served and database.

23. RESOURCES AVAILABLE

Research Personnel. Investigators and key personnel will have undergone mandatory education in human research participants' protection. Educational systems are in place to ensure that all research staff have been through such training and are approved by the IRB Human Subjects department. The responsibilities of investigators and research personnel are as follows:

Principal Investigator. The Principal Investigator will be responsible for overall project governance at UMass, leadership of the Project Team at UMass, protocol development, informing the data analytic plan, and dissemination efforts through professional presentations and peer reviewed journal publications

Co-Investigator. The Co-Investigators will be responsible for collaboration with other MOUD providers in the region and overseeing communication between research staff and community MOUD providers. Other responsibilities include overseeing contingency

management plan development and implementation and advising the team on data management and quality assurance protocols.

Project Manager. The Project Manager will be responsible for managing daily operations of recruitment and enrollment including training and supervising the research assistants. They will manage all IRB related submissions, amendments, and reporting.

Research Assistant(s). The research assistant(s) will be responsible for reviewing the electronic health record dashboard each shift and documenting potentially eligible patients on a Screening Log. They will be responsible for enrolling participants conducting interviews and completing telephone outcome assessment services for the stud(ies).

Software Engineer. The software engineer will be responsible for programming and managing the OARSCM mobile application and ensuring all data is flowing correctly between the mobile application and the secure server. They will have access to identified data within the Q2i OARSCM secure server at AWS. This data will include the patient's name (first and last), DOB, email address, cell phone number, urine toxicology results, and attendance in treatment. PHI will be directly entered into the mobile application. Q2i will have access to the server via secure shell terminal sessions. The OARSCM mobile application does not store PII/PHI locally on the device.

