5. BACKGROUND*

See grant: "RESEARCH STRATEGY" (p.2-4) for details. The Procedures for Phase 2 have been modified from the original submission. Updated Procedures are as follows:

Procedures

Screening, recruitment, eligibility and training procedures are in C.2.1 and the Eligibility criteria document.

Randomization will occur following determination of eligibility using an urn procedure and stratifying on 1) other (than opioid) substance use disorder no/yes, 2) gender/sex, 3) race/ethnicity.

TAU with MyMAT (n = 51). In the acute care setting, the Behavioral Health Service run by Drs. [name] and [name] provides SBIRT for substance use disorders, including OUD. They provide SBIRT as part of TAU, including, when possible, warm handoff contact with outpatient MOUD treatment that includes a scheduled outpatient appointment, optimally within 48 hours of the ED visit. Patients randomized to this group will also receive MyMAT, a mobile application with opioid treatment educational content, as an attention control measure against OARS+CM. TAU outpatient suboxone treatment consists of urine toxicology screening, group/individual therapy, and MOUD prescription continent on drugnegative (except cannabis, which is legal in MA) urine toxicology. Treatment visits are typically, weekly in weeks 1-4 and then taper over time, to every other week in weeks 5-8, and monthly in weeks 9-12 and thereafter. Nonadherence can lead to increased frequency/intensity of therapy and urine toxicology until the patient stabilizes. If increased frequency/intensity is unsuccessful, patients may be referred to detoxification and subsequently re-admitted to outpatient care when appropriate.

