Group A: TAU with MyMAT. For TAU participants, the usual care provided to individuals with OUD at the UMass University and Memorial hospitals will be provided. This typically consists of (1) medical stabilization and treatment, as needed; (2) brief counseling and referral to treatment by a social worker or other behavioral health provider, which includes providing a tailored referral list; and (3) when the patient is interested and treatment facility available, a "warm handoff" comprised of contact with the outpatient provider and transportation directly to the facility or a scheduled intake appointment within 48 hours, when feasible. TAU participants will also receive MyMAT, a mobile application with opioid treatment educational content, as an attention control measure against OARS+CM.

Group B: OARS+CM. Participants assigned to OARS+CM will receive the same treatment as in the TAU condition but with the enhancement of the CM features, described in detail in Section C.2.1, Proof-of-concept testing for usability section.

Table 1: Eligibility criteria						
Inclusion	Exclusion					
→ >= 18 years old	 Persistent altered mental status (not alert, not oriented, psychotic). 					
◆ Presenting for acute care at UMass University and Memorial hospitals, including EDs, inpatient medical units, inpatient behavioral health units, or community acute care partners for opioid addiction related health complaints, including opioid overdose, opioid related medical consequences, opioid intoxication or withdrawal syndromes, and/or seeking help for OUD	Patient declines referral to UMass Bridging MAT Clinic, to CleanSlate Addiction Treatment Center, to SaVida Health, to Eleanor Health, or to Spectrum Health Systems for MOUD.					
 Presence of a current DSM-V opioid use disorder (OUD), mild to severe 	 Not interested or willing to participate in MOUD treatment 					
 Medically appropriate for outpatient MOUD treatment, as judged by the 	 Unwilling to use the OARS+CM app (if assigned) 					
treating clinician and behavioral health consultant or toxicologist working with the patient clinically	 Does not have access to their own smartphone with at least iOS 7.1 or Android 4.2, the minimal technology required to run the app, or not willing to access clinic- dedicated computer to access the program 					

	Currently a UMMS student			
 Treatment provider of patient who 	 Prisoner or currently in state custody or 			

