11. PROCEDURES INVOLVED*

Measures: For Phase 1, the System Usability Scale (SUS) (patients and clinicians), Timeline Followback (TLFB) (patients only), and Addiction Severity Index (ASI) (patients only) will be used and is included in this submission. For Phase 2, The Mini Quiz (MQ), Mini-Usability Acceptability Testing (Mini-UAT) questionnaire, Timeline Followback (TLFB), PROMIS Pain Intensity and Interference Scales (PIIS), HIV Risk Behavioral Scale (HRBS), Post-traumatic Stress Diagnostic Scale for DSM-5 (PDS), Treatment Satisfaction Scale (TSS), and the System Usability Scale (SUS) will be used and are included in this submission.

Assessments/Procedures for Phase 2	Intake	Onboarding	Transition to Suboxone	Week 1 to 12	Month 1	Month 3 / End of Tx	Month 6
Mini Quiz, Patient form, OUD	X						
Mini-UAT, Service Utilization, TLFB	X				Х	Х	Х
PIIS, HRBS, PDS, U-Tox	X				Х	Х	Х
Healthcare Utilization	X						Х
App training, warm hand-off scheduling outpatient Suboxone intake		Х					
Monitor completion of MOUD intake			Х				
MOUD TAU / OARS+CM				Х			
Monitor treatment attendance/u-tox				X			
Treatment satisfaction, SUS*						Х	

^{*}Only for OAR+CM group

Phase 1: Aim 1 (Develop OARSCM): 30 Clinicians (20 user testing, 10 dyads) and 30 Patients

- 1a. After the OARSCM is developed, patients meeting criteria and consenting to participate will be guided through using the mobile application on their personal smartphone. If the participant's smartphone is not available for use to complete the instructed tasks, the participant will be able to use a study-provided iPad.
- 1b. Clinicians not associated with a specific patient participant verbally consenting to participate after reviewing the User Testing Fact Sheet will be guided through using the provider portal using a test account on a study provided computer in a private office.
- 1c. Clinicians working at the UMass Bridge Clinic, at the CleanSlate Addiction Treatment Center at SaVida Health, and at Spectrum Health Systems associated with a patient participant (considered a dyad) verbally consenting to participate after reviewing the Dyad Fact Sheet will receive an in-person or virtual training on the provider portal on a study provided computer in a private office. After the training, the clinician will provide standard MAT treatment to patient participants and use the OARSCM provider portal to track treatment.

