Phase 2 Aims 1 & 2 (RCT of OARSCM): Patients will complete a screening survey to assess for minimal eligibility criteria and confirm their interest. If a potential participant is deemed ineligible for the study, they will be informed that they are not a good fit for this study and the screening form will be shredded immediately after the encounter. After the RA consents the participant, they will open a randomization envelope and randomize the patient to either TAU or OARSCM. For TAU the participant will receive SBIRT provided by the RA, a warm handoff to a community MOUD treatment facility and will be trained on how to use MyMAT (an educational mobile application). For OARSCM the participant will receive TAU as described

above with the addition of the OARSCM mobile application instead of MyMAT. Participants will be trained on how to use the OARSCM mobile application, potentially earning prizes throughout treatment as part of contingency management. After leaving the ED, participants will complete follow-up calls at 1, 3, and 6-month time periods.

In Phase 2, all participants will receive an initial \$25 remuneration for enrollment during their ED visit, an additional \$30 per follow-up call (1 and 3 months), and an additional \$35 for completing the 6-month follow-up call for a total of \$120/participant. Those randomized to the contingency management group have to opportunity to earn additional money as part of treatment. See grant: "RESEARCH STRATEGY" (p12) "Procedures" for further details.

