Sample size justification. We use the proportion of participants who complete the Suboxone intake to start treatment as the calculating indicator. Based on the findings from a large randomized clinical trial on MAT treatment for opioid dependence after an acute care visit,¹⁵⁸ we estimate the proportion of patients who will initiate MAT at baseline is about 35%. We hypothesize that OARS will increase the rate by 25% and OARS+CM will increase the rate by 50%. Using G-Power program (proportions procedure) with $\alpha=0.05$, $N=150$ (50 each group), the calculated statistical power is >0.80 for the comparisons between TAU and OARS, TAU and OARS+CM, and OARS and OARS+CM.

Aim 2 is to assess the efficacy of OARS+CM for increasing Suboxone treatment adherence and abstinence outcomes. Main outcomes will be the percentage of opioid-free urine toxicology tests, and the percentage of group/individual therapy sessions attended. Secondary outcomes will be the longest duration of abstinence (LDA) outcome, measured at month 1, month 3 (end of study period) and month 6 (end of follow-up period), and sustained abstinence from Suboxone start through each follow-up. LDA and sustained abstinence will be as a composite of the greatest number of days with consecutive negative urine samples and self-reported no use; a composite of biochemical evidence and subjective report is needed because urine tests are too infrequent in the clinical setting to rigorously determine sustained abstinence based solely on biochemical evidence. Sustained abstinence and LDA are usually non-normally distributed and will be examined accordingly. We will assess the effect of the intervention using linear mixed model, controlling for the dependence of repeated measures and the clustering effects.

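### The research assistant role that opens the allocation envelope also takes the telephone self-reports behind sustained abstinence and longest duration of abstinence, with no masking or separation of staff described

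*Protocol*

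**What the plan says.** **Allocation.** Protocol section 24 (Phase 2 Aims 1 & 2) says that after consent the RA takes the next step: "they will open a randomization envelope and randomize the patient to either TAU or OARSCM". The role therefore knows the arm.

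**Outcome assessment.** Protocol section 23 lists the duties of the research assistant(s): "They will be responsible for enrolling participants conducting interviews and completing telephone outcome assessment services". Section 11 (Phase 2, step 5) sets these calls at 1, 3 and 6 months and centres them on substance use, opioids above all.

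**Use of self-report.** The SAP's Aim 2 paragraph builds LDA and sustained abstinence from negative urine samples together with self-reported no use. Its reason is that "a composite of biochemical evidence and subjective report is needed because urine tests are too infrequent". Sustained abstinence over 6 months is H2 in protocol section 4. The SAP calls both outcomes secondary.

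**Source of urine results.** Protocol section 6 takes biochemical verification from outpatient treatment records. Section 11 (step 6) expects some participants to have no such result at a follow-up point and turns to the prescription-monitoring record for them.

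**App items.** In the section 11 schedule, the Mini-UAT shares a row with the Timeline Followback (TLFB) at intake and months 1, 3 and 6. A separate row, "Treatment satisfaction, SUS", is marked at month 3 only, and its starred item is footnoted as OARS+CM only.

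**Who delivers SBIRT.** Section 24 says: "For TAU the participant will receive SBIRT provided by the RA". Section 5 says of the Behavioral Health Service: "They provide SBIRT as part of TAU". Section 6 describes usual care as "brief counseling and referral to treatment by a social worker or other behavioral health provider".

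**The concern.** An interviewer who knows the arm can probe differently, and a participant can shade an answer to suit the person asking. In this trial only OARS+CM participants earn prizes for opioid-negative urine (protocol section 5). Some of them may connect admitting use on the telephone with those prizes, and no call script is described that tells them otherwise.

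The effect would fall where urine evidence is thinnest. Usual-care visits become monthly from week 9 (section 5), so self-report carries more of the evidence in the later part of the 6-month window for H2. The prescription record shows MOUD prescriptions, so it cannot contradict a false report of no opioid use.

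The conflict-of-interest plan in section 3 restricts one investigator's part in enrolment, consent and analysis but does not cover outcome assessment. Section 32 says the data will support a device submission.

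**Working it through.** The plan states no figure on this point, so there is none to reproduce. The check is first textual, then an illustration of size.

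**Step 1: what the text establishes.**

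| Question | Answer in the documents |
|---|---|
| Does the allocating role know the arm? | Yes: the RA opens the envelope (section 24) |
| Does that role take the outcome calls? | Yes (section 23) |
| Must the same individual do both? | No: section 23 assigns duties to a role that may have several members |
| Is masking, staff separation or question order stated? | No, in either document |
| Does the RA deliver the experimental component? | Not shown. SBIRT goes to both arms: "For OARSCM the participant will receive TAU as described". Phase 2 app training names no trainer; the RA is named as trainer only for Phase 1 |
| Do app items reveal the arm? | The SUS would, at month 3 only. The Mini-UAT has no arm restriction, both arms have an app, and its content is not given |
| Which outcomes use abstinence self-report? | LDA and sustained abstinence. Not intake scheduled or completed (primary), nor percentage of opioid-free urine tests or of sessions attended (main Aim 2) |

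**Step 2: illustrative size.** All three inputs are assumptions; the documents give none of them.

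- p, true sustained abstinence, equal in both arms: 0.20 to 0.40
- u, share of non-abstinent participants with no urine result: 0.5
- d, additional share of those participants who deny use in OARS+CM compared with TAU: 0.05 to 0.15

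It is further assumed that self-report alone decides the composite when urine is missing.

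Only people who used can deny use, so overstatement = (1 - p) × u × d.

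| p | d = 0.05 | d = 0.10 | d = 0.15 |
|---|---|---|---|
| 0.20 | 0.80 × 0.5 × 0.05 = 2.0 points | 4.0 points | 0.80 × 0.5 × 0.15 = 6.0 points |
| 0.40 | 0.60 × 0.5 × 0.05 = 1.5 points | 3.0 points | 0.60 × 0.5 × 0.15 = 4.5 points |

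The range is 1.5 to 6 points.

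**Step 3: effect on false positives.** Take 51 per arm, a simple two-proportion test with pooled variance, two-sided 0.05 (the SAP does not state sidedness) and no true effect. Let p2 = p + overstatement. The chance of a significant result favouring OARS+CM is Φ[(p2 - p - 1.96 × SE0) / SE1], where SE0 uses the pooled rate and SE1 the separate rates.

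- Largest case: p = 0.20, p2 = 0.26, SE0 = 0.0833, SE1 = 0.0831. This gives Φ(-1.24) = 10.7%.
- Smallest case: p = 0.40, p2 = 0.415, SE0 = 0.0973, SE1 = 0.0973. This gives Φ(-1.81) = 3.5%.

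The nominal rate in that direction is 2.5%. The SAP plans mixed models, so these figures are only a guide.

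**The case against.** The strongest reply has five parts.

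1. **Role, not person.** A reader might infer that whoever delivered the intervention to a participant later asks that participant about drug use. The documents do not support this. They name a role, give SBIRT to both arms, assign SBIRT to different staff in different sections, and leave the Phase 2 app trainer unnamed. This part stands in full.

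2. **Arm-revealing items in every call.** A reader might infer this from the schedule, but only the SUS is arm-specific, and only at month 3. A shared table column shows neither that it is asked in the call nor that it comes before the TLFB. This stands too.

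3. **Biochemical check.** The schedule lists urine toxicology at months 1, 3 and 6, and a positive result would break a false claim of abstinence. The SAP does not say that self-report alone counts when urine is missing. This limits the size. It does not remove the exposure: follow-up is by telephone, results come from clinic records, and section 11 plans for participants who have none.

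4. **Size.** Multiplying one half by 5-15 points gives 2.5-7.5 points, but that treats everyone as able to conceal use and omits the factor (1 - p). The direction is also assumed. Participants cannot be masked to their app or prizes, and those prizes belong to a 12-week programme that ends before month 6.

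5. **Unseen sources.** Endpoint and procedure details are deferred to grant pages that were not available, and a masking rule may be written there. If so, a sentence carrying it into the protocol settles that part.

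What survives is narrower: allocation and outcome assessment share a role, and no safeguard is stated.

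**Conclusion.** The point holds in limited form. The role that learns the allocation also collects the self-report used in LDA and sustained abstinence, and neither document masks the caller, separates the staff or orders the questions. The conclusion concerns what the plan permits, not what it requires of any individual.

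Under the stated assumptions the overstatement of sustained abstinence is about 1.5-6 points, and the chance of a falsely significant benefit is about 3.5-11% in place of 2.5%. Those figures rest on assumed rates of missing urine, denial and abstinence, and on self-report deciding the composite when urine is absent. A masked caller would remove only part of the bias.

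It would be wrong to read this as a threat to the trial's primary result. The primary and main Aim 2 outcomes do not depend on abstinence self-report. It is worth acting on because H2 is a named hypothesis and the remedy costs little.

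**What to change.** Amend protocol section 11 (Phase 2, step 5) and section 23 (Research Assistant(s)):

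1. In every call, ask the TLFB and service-use items first and the app items (Mini-UAT, SUS, treatment satisfaction) last.
2. Read a fixed statement that call answers are not shared with the clinic and do not affect prizes, after confirming that this is true of study procedures.
3. Where more than one RA is available, give the call to one who did not enrol or randomise that participant, with the arm field hidden in REDCap until the TLFB is saved.

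Items 1 and 2 work with a single RA. Separately, reconcile sections 5, 6 and 24 on who delivers SBIRT.

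The cost is a reordered call script, a REDCap display setting and some scheduling. The downside is less continuity between participant and caller where item 3 applies.
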